2.5.2 Protocol deviation

The number and percentage of patients with protocol deviations will be tabulated by category and deviation for the FAS. Patients with protocol deviations will be listed with date and study day of occurrence, deviation and severity codes for the ENR.

The number of patients included in each analysis set will be tabulated for all screened patients. Reasons for exclusion from analysis sets will be tabulated for the ENR. Patient exclusion from analysis sets will be listed for all patients with reasons for exclusion (i.e., both protocol and non-protocol deviations).

2.5.3 Demographic characteristics

Demographic and Baseline characteristics will be listed and summarized descriptively overall patients on the FAS and the SAF.

The following demographic and vital signs variables collected in the eCRF at Baseline will be summarized:

1. Sex (Male, Female)
2. Age (in years)
3. Age category (< 50, 50 - 65, 65 - 75, 75 - 85, \geq 85)
4. Study eye (Left [OS], Right [OD])
5. Vital signs (sitting systolic/diastolic blood pressure [mmHg], sitting pulse rate [bpm])

2.5.4 Baseline characteristics

The following Baseline characteristics collected in the eCRF at Baseline will be summarized for study eye and fellow eye (wherever applicable):

- Study eye status at nAMD diagnosis (date of diagnosis, BCVA at diagnosis, CSFT at diagnosis)
- Time since nAMD diagnosis
- Time since nAMD diagnosis (month) (< 2.5 - 5, 5- 8, 8-11, 11-18)
- Unilateral versus bilateral nAMD
- BCVA
- BCVA (\leq 55, 56 - 70, \geq 71)
- BCVA categories (Count fingers, Hand motion, Light perception, No light perception) in case BCVA score is 0

[REDACTED]

[REDACTED]

[REDACTED]

[REDACTED]

- SD-OCT (analyzed by Duke [CRC])
 1. Lesion type (only at Baseline) (type 1, type 2, type 3)
 2. CSFT (μm)
 3. Baseline CSFT (< 300, ≥ 300 - 450, ≥ 450 - < 650, ≥ 650 [μm])
- Presence of fluid (Yes/No)
 1. Intraretinal fluid
 2. Subretinal fluid
 3. Sub-RPE fluid
- Volume (mm³) and height (μm) of each fluid (in case of presence)
 1. Intraretinal fluid
 2. Subretinal fluid
 3. Sub-RPE fluid
- In case of sub-RPE/PED: nature: serious PED/fibrovascular PED / mixed PED
 - 1. CNV lesion area (at the biggest surface) (mm²/μm²)
- Ophthalmic abnormalities (Yes, No)
 - 1. Disease activity assessment (Present)
 - 2. History of primary diagnosis:
 1. Disease (Neovascular Age-Related Macular Degeneration)
 2. Age of diagnosis
 3. Eye (OD, OS)
 4. Ongoing (Yes, No)
 - 3. History or evidence of the following in the study eye within the 90-day period prior to Screening/Baseline:
 1. Intraocular or refractive surgery
 2. Previous panretinal and peripheral laser photocoagulation

- 3. Previous macular surgery or other intraocular surgical intervention
- Concomitant medication at Baseline
- Medical history
- Co morbidities
- Current medical condition

2.5.5 Relevant medical history/current medical condition

Medical history/current medical conditions (general and ocular) will be coded using the Medical Dictionary for Regulatory Activities (MedDRA) terminology. History/conditions will be summarized for the FAS by primary system organ class (SOC), preferred term (PT) by eye (study eye and fellow eye). Verbatim recorded history/conditions will be listed together with the coded terms, date of diagnosis/surgery and whether the problem was ongoing at start of the study. The ongoing medical history will be considered as co morbidities. The co-morbidities will be summarized and listed separately for eye (study eye and fellow eye).

2.6 Treatments (study treatment, rescue medication, concomitant therapies, compliance)

2.6.1 Study treatment exposure

Extent of exposure to study treatment is calculated as the number of IVT injections received.

The following summaries will be presented:

1. Summary statistics of number of injection (n, q1, median, q3, min and max) will be provided.
2. Number of injections (n, q1, median, q3, min and max) before or at Week 8 and greater than Week 8.
3. Number of injections (n, q1, median, q3, min and max) before or at Week 16 and greater than Week 16.
4. Number of patients with injection category (1 injection, 2 injections up to the maximum number of injections) from Baseline to the end of the treatment period (Week 44/46) will be presented.
5. Treatment exposure by visit: The number and percentage of patients who received injections, missed a treatment and missed visits will be presented by visit.
6. The number of time the injection interval shorting and the number of time the injections interval increasing.
7. Summary statistics (n, mean, std, q1, median, q3, min and max) for overall duration will be provided.

The number and percentage of patients for changes in brolucizumab 6 mg treatment patterns over time (i.e. treatment interval adjustments, interruptions or permanent discontinuations) along with reasons, will be summarized. Discontinuations and primary reasons for treatment and/or study discontinuation will also be described.

Exposure data will be summarized on the SAF. The exposure data will be listed on the FAS.

2.6.2 Prior, concomitant medication and procedures

Each medication/therapies has the start and end dates recorded on the eCRF. Prior medications/procedures are defined as those medications/procedures which were taken/done and stopped prior to the first dose of study treatment. Concomitant medications/procedures are defined as any medication/procedures given at least once between the day of first dose of study treatment and the last day of study visit, including those which were started pre-baseline and continued into the treatment period. The below summary tables will be reported:

- Prior medication/procedures
- Concomitant medications/procedures which started prior to first dose of study treatment
- Concomitant medications/procedures which started on/after first of study treatment

All prior and concomitant medications will be coded using the most recent version of the WHO drug dictionary. All concomitant medications/procedures (general and ocular) will be listed and summarized in alphabetic order according to Anatomical Therapeutic Chemical (ATC) classification system and PT. Tables will also show the overall number and percentage of patients receiving at least one treatment of a particular ATC.

For prior and concomitant ocular medications, as well as ocular procedures performed during the study, separate tabular summaries will be prepared for the study eye and the fellow eye. A listing of all prior and concomitant medications and concomitant procedures will be provided.

For AESIs, a separate summary of prior and post aVEGF procedures will be provided.

For handling of missing or incomplete start and end dates, see [Appendix 5.1.3](#) of this document.

All summaries will be performed on the Safety set.

2.6.3 Prior and concomitant surgeries and procedures

All prior and concomitant surgeries and procedures indications will be summarized and listed by category (general, ocular) and eye (study and fellow).

For handling of missing or incomplete start and end dates, see [Appendix 5.1.3](#) of this document.

All summaries will be performed on the Safety set.

2.6.4 History of anti-VEGF therapy

The anti – VEGF therapy will be collected in CRF at Baseline. All recent anti – VEGF therapy will be listed and summarized. Table will present nature of the previous antiVEGF, summary statistics for total number of previous IVTs, number of patients and percentages of previous antiVEGF (3,4,5,6...), summary statistics for time since first antiVGEF, time since last antiVEGF along with below interval summary statistics.

1. Inclusion vs last antiVEGF
2. Last antiVEGF and second antiVEGF
3. Second last antiVEGF and third last antiVEGF

The listing will include nature of the previous antiVEGF, date of the last anti VEGF treatment, interval of the last anti VEGF treatment, date of the second last anti VEGF treatment , interval of the second last anti VEGF treatment, date of the third last anti VEGF treatment, interval of the third last anti VEGF treatment, date of the first anti VEGF treatment, interval of the first anti VEGF treatment and total number of anti VEGF treatments (including the last one).

The below characteristics prior to first antiVEGF will be summarized.

1. The summary statistics of BCVA and CSFT.
2. Number and percentage of IRF, SRF and Sub-RPE.
3. Summary statistics of height for IRF, SRF, Sub-RPE (if available).

The listing of above last antiVEGF characteristics will include patients identification number, therapies name and date of therapy, BCVA, CSFT, IRF, SRF, Sub-RPE and height for IRF, SRF, Sub-RPE (if available). The above analysis will be performed on the Safety set.

2.7 Analysis of the primary objective

2.7.1 Primary endpoint

The primary objective of this study is to evaluate the effect of brolucizumab 6 mg on disease control. The primary efficacy endpoint is the proportion of patients with no disease activity at Week 16 in the study eye.

Estimation for the proportion of disease control involves only calculating the ratio of successes. In this study

Event: 1= no disease activity (disease control)
0= disease activity (failure)

Count: Frequency or number of patients with no disease activity (disease control) at Week 16.

Proportion: Number of patients with no disease activity (disease control) at Week 16/Total number of patients in the FAS.

The number of disease control patients at Week 16, total number of evaluable patients, percentage of disease control and 95% confidence interval (CI) using the Clopper-Pearson method will be provided.

Sensitivity analysis will be performed for the primary endpoint using last observation carried forward (LOCF) method and considering disease activity for missing data at Week 16.

The above analysis will be done on the FAS and only on the study eye.

The analysis will be performed on the PPS, if there is more than a 10% difference in patients, between FAS and the PPS.

2.7.2 Supportive analyses

Subgroup analysis according to patient characteristics, like gender (male, female), age class (< 50, 50 - 65, 65 - 75, 75 - 85, \geq 85), Baseline fluids type (IRF, SRF, both), number of previous antiVEGF injections (3, 4 - 6, 7 - 9 and \geq 10), interval (in week) since previous antiVEGF

injection (4, 5, 6, 7, 8 and >8), and time since nAMD diagnosis (2.5 – 5 month, 5 - 8 months, 8 - 11 months, 11 - 18 months and > 18 months).

2.8 Analysis of secondary efficacy objectives

2.8.1 Secondary endpoints

2.8.1.1 Long-term disease activity criteria

Not applicable for IA.

2.8.1.2 Optical coherence tomography (OCT)

The following secondary efficacy parameters based on OCT will be analyzed as given below.

2.8.1.2.1 Central sub-field retinal thickness (CSFT)

The summary statistics of central sub-field retinal thickness (CSFT) measured by OCT for nAMD patients, change and percentage change from Baseline in CSFT will be presented by visit along with first anti VEGF Treatment CSFT.

The number and percentage of patient with CSFT category (< 300, \geq 300 - 450, \geq 450 - < 650, \geq 650 [μ m]) will be presented by visit along with first anti VEGF Treatment CSFT.

The above analysis will be done on the FAS and only on the study eye.

2.8.1.2.2 Presence of fluid (Yes/No)

The number and percentage of patients with fluid as shown below will be presented by visit along with first anti VEGF Treatment.

1. Intraretinal fluid
2. Subretinal fluid
3. Sub-RPE fluid
4. Without any fluid (IRF/SRF/sub-RPE)
5. In case of sub-RPE/PED: nature: (serious PED/fibrovascular PED/mixed PED)

Volume (mm^3) and height (μm) of intraretinal fluid, subretinal fluid and/or sub-RPE fluid will be presented the summary statistics (n, mean, std, median, min and max) by visit, if available.

The above analysis will be done on the FAS and only on the study eye.

2.8.1.2.3 Dry retina

The proportion of patients without both fluids (IRF and SRF), without IRF, without SRF, without sub-RPE will be presented by visit, separately, up to Week 16

The 95% confidence interval (CI) for proportion using the Clopper-Pearson method will be provided by visit and overall.

The above analysis will be done only on the FAS and on the study eye.

2.8.1.2.4 Time to dryness

Not applicable for IA.

2.8.1.2.5 Maximum duration of dryness

Not applicable for IA.

2.8.1.3 Durability

2.8.1.3.1 Last interval

Not applicable for IA.

[figure not shown]
2.8.1.3.2 Maximal interval

Not applicable for IA.

2.8.1.4 Function outcomes (Best Corrected Visual Acuity (BCVA))

Summary statistics (n, mean, std, median, min and max) of BCVA for nAMD patients will be presented along with change from Baseline in BCVA by visit along with first anti VEGF Treatment BCVA.

The above analysis will be done on the FAS and only on the study eye.

2.10 Safety analyses

Safety measurements include duration of exposure, vital signs, and adverse events (AEs). All safety endpoints will be summarized using the Safety Set. Patients will be analyzed according to the treatment received. No imputation will be carried out for missing data.

2.10.1 Adverse events

All information obtained on AEs will be displayed by patient Summary tables for AEs will summarize only on-treatment events, with a start date during the on-treatment period ([see Section 2.1.1](#)) for definition of on-treatment period).

The count of treatment-emergent AEs, number (and percentage) of patients with treatment-emergent AEs (defined as events started after the first dose of study treatment or events present prior to start of study treatment but increased in severity based on PT) will be summarized in the following ways:

- By primary SOC and PT.
- By primary SOC, PT and maximum severity.

Separate summaries will be provided for study treatment related AEs, study procedure related AEs, death, SAEs, other significant AEs action taken leading to study treatment withdrawn and AEs leading to dose interval adjustment (interval increase, interval reduce). Separate summaries will be provided for AESI.

Adverse events will be summarized by presenting, the number and percentage of patients having any AE, having an AE in each primary SOC and having each individual AE (PT). Summaries will also be presented for AEs by severity. Summaries for AE will be presented for study treatment and procedure related to AEs. If a patient reported more than one AE with the same PT, the AE with the greatest severity will be presented. SOC will be presented in alphabetical order, preferred terms will be sorted within SOC in descending frequency of AEs. If a patients reported more than one AE within the same primary SOC, the patient will be counted only once with the greatest severity at the SOC level, where applicable. The AE will be presented in separate sections of ocular and non-ocular. For ocular then it will be presented by study eye, fellow eye, and any eye.

Separate summaries will be presented for ≤ 16 weeks and > 16 weeks.

For the legal requirements of ClinicalTrials.gov and EudraCT, 2 required tables on treatment emergent AEs which are not SAEs with an incidence greater than 5% and on treatment emergent SAEs and SAEs suspected to be related to study treatment will be provided by system organ class and PT on the safety set population.

If for a same patient, several consecutive AEs (irrespective of study treatment causality, seriousness and severity) occurred with the same system organ class and PT:

- A single occurrence will be counted if there is ≤ 1 day gap between the end date of the preceding AE and the start date of the consecutive AE.
- More than one occurrence will be counted if there is > 1 day gap between the end date of the preceding AE and the start date of the consecutive AE.

For occurrence, the presence of at least one SAE / SAE suspected to be related to study treatment / non SAE has to be checked in a block e.g., among AE's in a ≤ 1 day gap block, if at least one SAE is occurring, then one occurrence is calculated for that SAE.

The number of deaths resulting from SAEs suspected to be related to study treatment, procedure and SAEs irrespective of study treatment relationship will be provided by SOC and PT.

In addition, all treatment emergent AEs and SAE will also be listed.

The by-patients listing will include: SOC/PT/Verbatim term, start date, end date, severity, relationship to study treatment and procedures, whether or not it is a SAE, action taken with study treatment and outcome; duration will be calculated as (end date – start date + 1) and for ongoing AE (last visit date – start date + 1) by ocular and non-ocular. For ocular then it will be presented by study eye, fellow eye and any eye.

A summary of action taken with number and percentage of patients will presented with treatment interrupted, treatment withdrawn, not applicable and unknown.

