1.2 Study objectives and endpoints for interim analysis

The study objectives and endpoints as per protocol are presented in [Table 2-1](#); those that are being assessed for the IA are marked (with ‡) with relevant flag denoting assessment at Week 16 as applicable.

This IA is planned to evaluate applicable efficacy and safety endpoints for patients who have completed Week 16 evaluations.

Table 2-1 Objectives and related endpoints

Objectives	Endpoints
Primary objective	Endpoint for primary objective
• To evaluate the effect of brolucizumab 6 mg on disease control	• Proportion of patients with no disease activity at Week 16 ‡
Secondary objectives	Endpoints for secondary objectives
• To evaluate the long-term effects of brolucizumab 6 mg on disease control	• Proportion of patients with no disease activity at Week 48 §
• To evaluate the effect of brolucizumab 6 mg on anatomical parameters	• Change from Baseline in CFST as assessed by OCT over time up to Week 48 ‡ • Absence of IRF, SRF, and sub-RPE fluid as assessed by OCT over time up to Week 48 ‡ • Proportion of patients with a dry retina (neither IRF nor SRF) up to Week 48 ‡
• To evaluate the durability of brolucizumab 6 mg	• Distribution of the last interval with no disease activity up to Week 48 § • Distribution of the maximal intervals with no disease activity up to Week 48 §
• To evaluate functional outcomes	• Average change in BCVA from Baseline up to Week 48 ‡
• To assess the safety and tolerability of brolucizumab 6 mg	• Incidence of AEs (serious and non-serious) up to Week 48 ‡

§ These endpoints will not be assessed for the IA.

‡ These endpoints will be assessed for the Week 16 timepoint only for the IA.

AEs=adverse events, BCVA=best corrected visual acuity, [REDACTED] CSFT=central sub-field retinal thickness, [REDACTED] IRF=intraretinal fluid, OCT= optical coherence tomography, [REDACTED]
[REDACTED] SRF= subretinal fluid.

2 Statistical methods

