Percent change from Baseline: The percent change from baseline will be calculated as below: $((\text{post-baseline value} - \text{Baseline value}) / \text{Baseline value}) * 100$.

Proportion: A proportion refers to the fraction of the total that possesses a certain attribute. In this study attribute is disease free activity.

Disease control: When patients will have no disease activity after taking study treatment then patient will be consider as disease control.

On-treatment period: The on-treatment period lasts from the date of first administration of study treatment to 28 days after the date of the last actual administration of any study treatment.

Treatment duration: The maximum planned duration of treatment for each patient is 44 to 46 weeks in accordance with the designated treatment regimen. Discontinuation of study treatment for a patient occurs when study treatment is stopped earlier than the protocol planned duration and can be initiated by either the patient or the investigator.

Treatment discontinuation: When patients discontinue study treatment but continue in the study, the efficacy data will be used at the time the patient stopped study treatment.

Last interval: The last treatment interval (defined by the investigator) before Week 48.

Maximum interval: The longest interval of treatment reached by the patient over the study period.

Event for no disease activity: When patients will be with no disease status as per investigator decision after last dose in initiation phase then the patients will consider as event for no disease activity. If patients with active disease status or early discontinue then patients will be considered as censored for disease activity.

Dry retina: Absence of fluid (IRF/SRF/ sub-RPE) will be considered as dry retina.

Event for dry retina: When patients have absence of fluid then it will be considered as an event of dry retina. If patients have a presence of fluid before/at EOS or early discontinuation then will be censored.

Study eye and fellow eye: The Investigator selects the eye with the worse BCVA at Screening as the study eye if both eyes are eligible as per the inclusion and exclusion criteria, unless the investigator deems as a study eye more appropriate to select the eye with better BCVA, based

on medical reasons or local ethical requirements. If both eyes are eligible as per the inclusion and exclusion criteria, then it is recommended to select the right eye as the study eye.

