2.2 Visit windows for data analysis

Visit windows will be used for the data analysis, as per the planned visits in the protocol. During the q4w/q8w/q12w phase, i.e., from Week 16 to Week 44, the treatment visit intervals will be determined by the investigator, based on the patient's disease activity.

For the interim analysis data collected up to Week 16 for the efficacy analysis and all safety data collected up to the interim data-cutoff for the safety analysis.

Table 2-1 Assessment windows for scheduled visits

Analysis Visit	Week	Scheduled Day	Visit Window
Screening/Baseline	BL	1	-14 days to Day 1*
Week 4	4	28	Day 22 – 34
Week 8	8	56	Day 50 – 62
Week 12	12	84	Day 78 – 90
Week 14	14	98	Day 92 – 104
Week 16	16	112	Day 106 – 118
Week 18	18	126	Day 120 – 132
Week 20	20	140	Day 134 – 146
Week 22	22	154	Day 148 – 160
Week 24	24	168	Day 162 – 174
Week 26	26	182	Day 176 – 188
Week 28	28	196	Day 190 – 202
Week 30	30	210	Day 204 – 216
Week 32	32	224	Day 218 – 230
Week 34	34	238	Day 232 – 244
Week 36	36	252	Day 246 – 258
Week 38	38	266	Day 260 – 272
Week 40	40	280	Day 274 – 286
Week 42	42	294	Day 288 – 300
Week 44	44	308	Day 302 – 314
Week 46	46	322	Day 316 – 328
Week 48	48	336	Day 330 – 342
Week 50	50	350	Day 344 – 356

* Baseline measurement before the first treatment administration.

The number of weeks between visits will vary depending on the disease activity and length of intervals between injections as determined by disease activity assessment. Study treatment at the optional inspection visits (6 weeks after the last injection when the interval is extended from 4 weeks to 8 weeks, 10 weeks after the last injection when the interval is extended from 8 weeks to 12 weeks, and 14 weeks from the last injection when the interval is extended from 12 weeks to 16 weeks) is at the discretion of the Investigator based.

According to the patient treatment schedule, the last treatment can be at Week 44 or to Week 46. If the last treatment visit is Week 46, the end of study visit will be at Week 50 (at least 4 weeks after the last injection) instead of Week 48.

If study visit assessments and the corresponding treatment occur on separate days, a repeat safety check-up should be performed prior to treatment of the eye and results documented in the source documents. If any safety concern arises related to the study eye that, in the opinion of the investigator, may be further impacted by the study treatment or injection procedure,

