2.3 Analysis sets

The Enrolled Set (ENR) includes all patients who signed an ICF and are assigned patient numbers.

The Safety Set (SAF) includes all patients who received at least one IVT injection of study treatment.

The Full Analysis Set (FAS) will be the same as the Safety Set in this study without protocol deviation with impact and will be used as primary population to analyze the efficacy endpoints.

The Per-Protocol Set (PPS) is a subset of patients in the FAS without PDs with impact. The list of PD criteria will be provided in edit checks specification (ECS) document.

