2.10.1.1 Adverse events of special interest / grouping of AEs

The number (%) of patients with adverse events of special interest (AESI) will be summarized by Standardized MedDRA Query and PT. A listing will also be provided.

A Case Retrieval Sheet (CRS) with the exact composition of the AE groupings is to be used to map reported AEs to the AESI groupings. This file may be updated (i.e. it is a living document) based on review of accumulating trial data, and therefore the groupings are also subject to potential change. The most up-to-date version of the CRS will be used at the time of the analysis.

The number and percentage of patients having any AESI, having an AESI in each SOC and having each individual AE (PT) will be presented.

The number and percentage of patients for AESI type along with incidence rate per patient and per 1000 injection will be provided. Incidence rate per patient is defined as number of patients in AESI type/total number of patients in safety analysis set and incidence rate per 1000 injection is define as (number of occurrence of AESI type/total number of injections)*1000.

The number and type of AESI will be plotted according to the time after last brolucizumab injection and time since first brolucizumab injection.

Summary statistics for change from baseline in BCVA after end date of AESI will be provided for each AESI type and change from baseline in BCVA will be plotted overall and for each type of AESI.

Patients demographics, baseline characteristics and medical history will be provided for AESI patient with safety set.

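### The interim SAP contradicts itself on whether adverse events after Week 16 are reported, and the > 16 weeks table would divide by the whole Safety Set, including patients with no countable time in that period

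*SAP*

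**What the plan says.** All references are to the interim SAP unless stated.

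**How far the safety data run.** Section 1.1 limits the interim to data up to Week 16 and sets the cut-off at 20-Oct-2022. In 1.2, Table 2-1 puts a double-dagger flag on adverse event incidence, and the footnote to that flag reads "These endpoints will be assessed for the Week 16 timepoint only for the IA". Section 2.4 lists time points no later than Week 16 for everything except demographics and baseline characteristics. Section 2.2, however, uses "all safety data collected up to the interim data-cutoff for the safety analysis". Section 2.6.1 asks for injection counts after Week 16, and 2.10.1 says "Separate summaries will be presented for ≤ 16 weeks and > 16 weeks". Section 4, on changes to protocol-specified analyses, is marked not applicable and resolves nothing.

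**What the percentages divide by.** Section 2.10 says "All safety endpoints will be summarized using the Safety Set", and 2.3 says "The Safety Set (SAF) includes all patients who received at least one IVT injection of study treatment". In 2.10.1, "Adverse events will be summarized by presenting, the number and percentage of patients having any AE"; no at-risk rule is given for the split at Week 16. For events of special interest, 2.10.1.1 is explicit: "Incidence rate per patient is defined as number of patients in AESI type/total number of patients in safety analysis set".

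**Which events count.** The tables in 2.10.1 include only events that start in the on-treatment period, which 2.1.1 ends "28 days after the date of the last actual administration of any study treatment".

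**The concern.** There are two problems. First, the content of the interim safety report depends on which sentence the programmer follows: either nothing after Week 16 is shown, or everything to the cut-off is shown. The interim SAP's introduction allows the results to be published, so the ambiguity can reach readers.

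Second, if the late table is produced, its numerator and denominator follow different rules. The numerator needs on-treatment time after Week 16; the denominator needs only one injection at any time. Early stopping is part of the design. Protocol 6.1.4 and 9.1.1 end study treatment for intraocular inflammation and for patients who require injections every 4 weeks after the initiation phase. Follow-up after Week 16 also differs between patients because the cut-off is a single calendar date. A reader who sets the two percentages side by side would be comparing periods with different numbers at risk and different lengths of observation. The documents treat dosing after loading as a central safety question (protocol 1.1 and 4.2), so the late figure will be looked at.

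**Working it through.** **Starting N.** The documents give no figure for late adverse events. The only number bearing on the size of the Safety Set is the sample size in protocol 12.8. With p = 0.30 and n = 265, the half-width is 1.96 × √(0.30 × 0.70 / 265) = 0.0552, which agrees with the tabled 0.055. With 10% dropout, 265 / 0.90 = 294.4, rounded up to 295. I use 295 as a stand-in for the Safety Set size N.

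**Who can have a counted late event.** Scheduled days come from Table 2-1 in interim SAP 2.2 (Week 8 = Day 56, Week 14 = Day 98, Week 16 = Day 112). The on-treatment period ends on the last injection day + 28.

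| Last injection | Period ends | Countable days after Day 112 |
|---|---|---|
| Week 8 | 56 + 28 = Day 84 | 0 |
| Week 14 | 98 + 28 = Day 126 | 14 |
| Week 16 | 112 + 28 = Day 140 | 28 |

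An earlier last injection also gives 0. With the 30-day tail of the final SAP, the Week 8 row ends on Day 86, with the same result.

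**Size of the denominator effect.** Let k be the number of patients with a late event and M the number with on-treatment time after Day 112. The table shows k/N and the at-risk percentage is k/M, so shown = at-risk × M/N. M is not in the documents. The shares below are assumptions; 90% uses the planned 10% dropout as a proxy, and k = 6 is for illustration.

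| M/N | An at-risk 5.0% is shown as | M if N = 295 | 6/N | 6/M |
|---|---|---|---|---|
| 95% | 4.75% | 280 | 2.03% | 2.14% |
| 90% | 4.5% | 266 | 2.03% | 2.26% |
| 80% | 4.0% | 236 | 2.03% | 2.54% |

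**Unequal follow-up.** With the cut-off on 20-Oct-2022, a patient whose Day 1 was 1-Jul-2022 is on Day 112 at the cut-off and has no later time. Only patients with Day 1 by 19-Nov-2021 reach Week 48 (Day 336). If accrual was uniform over 6 to 18 months ending 1-Jul-2022 (an assumption), the mean time observed after Week 16, before any discontinuation, is 13.0 to 25.4 of a possible 32 weeks.

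**Direction of the early versus late comparison.** Assume a constant, low risk, a full 16-week early window, and at-risk patients observed for the mean times above. Then late % / early % ≈ (M/N) × (mean late weeks) / 16. At M/N = 0.90 this is 0.90 × 13.0 / 16 = 0.73 for the short accrual and 0.90 × 25.4 / 16 = 1.43 for the long one. At 0.80 it is 0.65 and 1.27. An unchanged risk could therefore appear as a fall or as a rise.

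**The case against.** Several counter-arguments have force.

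- **The denominator is inferred.** Section 2.10.1 does not state one for the split, 1.2 speaks of patients who completed Week 16 evaluations, and the table shells are separate documents not seen here. This stands as a caution. Even so, the general rule in 2.10 makes the whole Safety Set the natural reading, and 2.10.1.1 states it outright for events of special interest.
- **k/N is a legitimate quantity.** It is the share of all treated patients with a late event. It is low only relative to patients still at risk.
- **An at-risk count is not a full cure.** It still mixes very unequal follow-up, and it is selected, because patients with intraocular inflammation must stop treatment. This stands, and it is why a rate on patient-time is needed as well.
- **Some of the information is elsewhere.** Section 2.5.1 reports how many are on treatment after Week 16, 2.6.1 counts injections after Week 16, and 2.10.1.1 gives a rate per 1000 injections. None of these is linked to the late table, and that rate is not said to be split at Week 16.

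Three stronger readings are tempting, and the documents do not support them. A reader might infer that this split is the only planned view of event timing. In fact 2.10.1.1 also plots events of special interest by time since the first and since the last injection, and 5.3 derives time since the last injection for confirmed events. A reader might infer that the denominator alone would produce an apparent fall in risk after loading. However, loading ends at Week 8, not Week 16, and the longer possible late window can outweigh the denominator effect, as the ratios of 0.65 to 1.43 show. Finally, a reader might suppose that a large share, such as 20% to 40%, has no late time. No source gives this. Patients stopped after an injection at Week 14 or 16 still have 14 or 28 countable late days, and the only related figure is 10% planned dropout.

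**Conclusion.** The contradiction on the safety data cut is plain from the text and needs no assumption. The denominator problem holds if 2.10 is applied as written: the late percentage falls short of the at-risk percentage by the factor M/N whenever some treated patients have no on-treatment time after Day 112. With M unknown, the size is illustrative: 5.0% becomes 4.5% at 90% at risk and 4.0% at 80%. The crude percentages for the two periods are not comparable, and the documents do not determine which way the comparison is distorted. The consequence is minor. The table is descriptive, no decision rule depends on it, and the final SAP (2.9.1) has no such split.

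**What to change.** 1. Amend interim SAP 1.1, the Table 2-1 footnote in 1.2, and 2.4 so that adverse events are reported to the data cut-off, in line with 2.2, 2.6.1 and 2.10.1.
2. For > 16 weeks, state the denominator as Safety Set patients with on-treatment time after Day 112 and before the cut-off. The whole Safety Set can remain the denominator for ≤ 16 weeks.
3. Give patient-years and exposure-adjusted rates for both periods, and split the rate per 1000 injections for events of special interest at Week 16.

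The cost is SAP wording and a little programming from data already collected; late percentages will be slightly higher. The final SAP (2.15) describes the interim as already performed, so in practice this may mean a corrected table or a footnote to the interim report.
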